Table 2: Study Procedures and Assessments (Continued)

	Prescreening	Screening	BL ^a	Escalation period (weeks)				Maintenance period (weeks)			Follow-up (weeks)		Unscheduled
Study week ^b	Up to 3 months	Up to 31 days	Day 1	1 (Day 7)	2 (Day 14)	3 (Day 21)	4 (Day 28)	6 (Day 42)	7 (Day 49)	8/ ET ^c (Day 56)	9 (Day 63)	10 ^d (Day 70)	
Visit window (days)			0	±3 days							±3 days from week 8		
Assess IMP accountability / compliance / supply				X ^w	X	X ^w	X	X ^w	X ^w	X			X ^j
Assess AEs		X	X	X	X	X	X	X	X	X	X	X	X
Concomitant medications		X	X	X	X	X	X	X	X	X	X	X	X

^a The baseline visit (day 1) will occur the same day as the scheduled first dose of the IMP (day 1).

^b Assessment will be performed at the end of study week (±3 days).

^c For patients who withdraw prematurely, an early termination visit should be conducted as soon as possible after the last dose of IMP. In addition, all patients who discontinue early will have a follow-up telephone contact for safety evaluation 2 weeks after their last dose of IMP; evaluations will be as described for week 10.

^d This visit is a telephone contact for safety evaluation, required only for patients who will not roll over into the open-label safety extension study for TEV-50717.

^e The screening visit may be conducted over 2 separate visits at the discretion of the investigator. If the screening visit is divided into 2 visits, the blood sample should be obtained during the first of the 2 visits.

^f Patients will be provided with a diary at baseline, week 2, week 4, and at unscheduled visits, to record critical information on dosing. The date and time of the last dose of study medication before the week 8 visit should be recorded in the diary by the patient or caregiver/adult. The site will document the date and time of the sample collection. Prior to the clinic visit on week 8, patients will be reminded to record the start time of their last meal and the time of their last dose in their diary.

^g Dose escalation will only occur during the dose escalation period (ie, from week 1 to week 4).

^h Weight must be measured with shoes and outerwear off.

ⁱ Orthostatic blood pressure and pulse will be measured after patient is in standing position for at least 3 minutes.

^j Assessment will be completed at investigator's discretion.

^k All ECGs will be performed after at least 5 minutes of rest in a supine or semi-supine position.

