^l Two samples will be collected. The first sample will be collected upon arrival at the clinic. The second sample will be collected within 2 to 3 hours after the first PK sample collection. Patients with early morning visits (ie, within 2 hours of their scheduled AM dosing) should take their IMP dose in the clinic after the first PK sample is collected.

Clinical Study Protocol with Amendment 03

- ^m The patient’s genotype for CYP2D6 will be blinded during the conduct of the study, except for the sample analysis and IRT vendor.
- ⁿ For females who are postmenarchal or ≥ 12 years of age, a urine test will be administered at baseline and at week 4, while a serum test will be administered at screening, week 8, and if clinically indicated.
- ^o MINI Kid (children and adolescents) modules to be used are Major Depressive Episode (Module A), (Hypo) Manic Episode (Module D), OCD (Module J), Alcohol Dependence/Abuse (Module L), Substance Dependence/Abuse (Non-alcohol; Module M), ADHD (Module O), Conduct Disorder (Module P), and Psychotic Disorders and Mood Disorders with Psychotic Features (Module R).
- ^p Children 6 years of age at baseline will not complete the self-report version; the caregiver/adult will complete the parent version.
- ^q For children 13 years of age and under, interviews may be performed separately or jointly with the caregiver/adult as appropriate or defined by the scale. For children over 13 years of age, caregiver/adult involvement is strongly encouraged. Questions should be directed to the child, but the caregiver/adult should be encouraged to add relevant information.
- ^r Input from the caregiver/adult is required.
- ^s The YGTSS, TS-CGI, TS-PGII, and [REDACTED] questionnaires should be performed before any blood draws or ECG assessments.
- ^t Perform assessment of Severity Ratings of the questionnaire. Inventory portions (ie, “Motor Tic Symptom Checklist” and “Phonic Tic Symptom Checklist” do not need to be performed).
- ^u Perform the Severity Ratings of OCD symptoms (Questions 1 through 10) only. Checklist does not need to be performed.
- ^v Contact IRT and dispense IMP and patient diary. Study drug will be dispensed in the clinic; patients will receive doses for 2 weeks (current dose level and next dose level) to cover the telephone contacts during escalation. See [Table 1](#) for baseline weight-based dosing titration. At week 4, patients will receive doses for 4 weeks of treatment.

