5.9. Randomization and Blinding

This is a Phase 3, randomized, double-blind, placebo-controlled, 8-week-treatment study in which patients with tics associated with TS will be invited to participate. Patients will be randomized to either TEV-50717 (low-dose, high-dose) or matching placebo in a 1:1:1 ratio using an Interactive Response Technology (IRT) based on their baseline weight and CYP impairment status. The patients will be stratified into 2 age groups (6 to 11 years and 12 to 16 years). Patients and investigators will remain blinded to treatment assignment during the study.

Patients will be centrally randomly assigned to the treatment groups by means of a computer-generated randomization list after confirmation of all eligibility criteria. The creation of the randomization list will be under the responsibility and oversight of Syneos Health.

In addition, the sponsor's clinical personnel and all vendors (with exception of the IRT vendor and the bioanalytical sample analysis vendor) involved in the study will be blinded to the IMP identity until the database is locked for analysis and the treatment assignment revealed. After unblinding of this study, the study site may remain blinded to patient treatment assignments until completion of the safety extension Study TV50717-CNS-30047.

The randomization list and treatment will be assigned to the relevant treatment groups through a qualified service provider (ie, via IRT). The generation of the medication list and management of the IRT system will be done by a qualified service provider under the oversight of Nuvelution TS Pharma, INC (referred to hereafter as Nuvelution TS Pharma).

The staff member at the investigational center who will dispense the IMP will not know the treatment given to each patient.

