5.11. Total Blood Volume

The total volume of blood to be collected for each patient in this study is approximately 35 mL, as detailed in [Table 4](#).

Table 4: Blood Volumes

Type of samples	Volume per sample	Total number of samples	Total volume (maximum)
Clinical laboratory (chemistry/hematology)	10 mL	2	20 mL
Pharmacokinetic	5 mL	1 time point (week 8) × 2 samples	10 mL
CYP2D6 genotyping	3 mL	1	3 mL
Optional pharmacogenetic sample	2 mL	1	2 mL
Total			35 mL

CYP2D6=cytochrome P450 2D6.

Note: beta-human chorionic gonadotropin testing (in females who are postmenarchal or ≥12 years of age) is included in the clinical laboratory sample.

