7.5.2. Other Clinical Laboratory Tests

7.5.2.1. Human Chorionic Gonadotropin Tests

β-HCG tests in serum or urine will be performed for all females who are postmenarchal or ≥12 years of age as detailed in [Table 2](#) and, if clinically indicated. Any female patient who becomes pregnant during the study will be withdrawn. Procedures for reporting the pregnancy are provided in Section [7.3](#).

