9.7. Safety Analysis

Safety endpoints for this study are as follows:

- adverse events and concomitant medications: from the signing of the informed consent/assent form through follow-up, inclusive of all visits and telephone contacts
- physical examination: screening and week 8
- neurological examination: screening and week 8
- vital signs: screening; baseline; and weeks 2, 4, 8, and 9
Note: orthostatic blood pressure and pulse at baseline and weeks 4 and 8
- children's C-SSRS
 - baseline/Screening scale: screening
 - since Last Visit scale: baseline, and weeks 2, 4, 8, and 9
- CDI-2 (Parent and Self-report Profiles): screening; baseline; and weeks 2, 4, 8, and 9
- 12-Lead ECG: screening, baseline, and weeks 4 and 8
- clinical laboratory tests (serum chemistry, hematology, and urinalysis): screening and week 8
- pregnancy testing: screening, baseline, and week 8
- drug screen: screening and week 8

Safety analyses will be performed on the safety analysis set (Section 9.2.3).

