- measure vital signs (orthostatic pulse and BP [after standing for at least 3 minutes], body temperature, and respiratory rate) and weight (Note: Weight must be measured with shoes and outerwear off.)

- perform 12-lead ECG (Note: ECG will be performed after at least 5 minutes rest in a supine or semi-supine position.)
- perform serum pregnancy (β -HCG) test (only in females who are postmenarchal or ≥ 12 years of age)
- administer the following questionnaires (Note: For C-SSRS, [REDACTED] and Child and Adolescent Gilles de la Tourette Syndrome - Quality of Life scale (C&A-GTS-QOL), children 13 years of age and under may be interviewed separately or jointly with the caregiver/adult as appropriate or defined by the scale. For children over 13 years of age, caregiver/adult involvement is strongly encouraged. Questions should be directed to the child, but the caregiver/adult should be encouraged to add relevant information. The YGTSS, TS-CGI, TS-PGII, and [REDACTED] questionnaires should be performed before any blood draws or ECG assessments.):
 - CDI-2, Parent and Self-report Profiles (Note: Children 6 years of age at baseline will not complete the self-report version; the caregiver/adult will complete the parent version.)
 - C-SSRS (children's Since Last Visit [SLV])
 - YGTSS (Input from the caregiver/adult is required.)
 - TS-CGI
 - TS-PGII (Input from the caregiver/adult is permitted.)
 - [REDACTED]
 - [REDACTED]
 - [REDACTED]
 - C&A-GTS-QOL
- dispense investigational medicinal product (IMP) (patients will receive doses for 2 weeks [current dose level and next dose level] to cover the telephone contacts)
- provide patients with a diary to record critical information on dosing
- assess of adverse events
- review concomitant medications

4. Procedures During Administration of Investigational Medicinal Product

a. Escalation Period (Weeks 1 and 3) and Maintenance Period (Week 6)

Patients who meet the inclusion and exclusion criteria at screening will continue to visit 1, when baseline assessments will be conducted. The YGTSS, TS-CGI, TS-PGII, and [REDACTED] questionnaires should be performed before any blood draws or ECG assessments.

The following procedures will be performed at weeks 1, 3, and 6:

- telephone contact
- dose escalation (weeks 1 and 3 only)
- assess IMP accountability/compliance/supply
- assess of adverse events
- review concomitant medications

b. Escalation Period (Week 2)

The following procedures will be performed at week 2:

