### 9.6. Pregnancy

Pregnancy tests will be performed for females who are postmenarchal or  $\geq 12$  years of age. Urine test will be administered at baseline, and serum test will be administered at screening and Week 8. The pregnancy data will be presented in a data listing.

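### Appendix B asks for a serum pregnancy test at baseline and week 4, where Table 2, the SAP and the blood-volume total all fit a urine test

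*Protocol*

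**What the plan says.** Appendix B has five pregnancy-test entries, for screening, baseline, week 4, week 8 and unscheduled visits. All five specify serum; the baseline and week 4 entries read "perform serum pregnancy".

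Footnote n of protocol Table 2 (Section 3.6) divides the visits. Serum is for screening, week 8 and where clinically indicated. For the other two visits, "a urine test will be administered at baseline and at week 4". Section 7.5.2.1 says that "tests in serum or urine will be performed for all females who are postmenarchal or" at least 12 years old, and refers to Table 2 for the detail.

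The SAP's Table 2 carries the same footnote. SAP Section 9.6 says: "Urine test will be administered at baseline, and serum test will be administered at screening and Week 8". It does not mention week 4. Protocol Section 9.7 also leaves week 4 out of its list: "pregnancy testing: screening, baseline, and week 8".

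The note under Table 4 (Section 5.11) says that HCG testing "is included in the clinical laboratory sample", a sample that Table 4 counts twice.

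**The concern.** Both texts are current and operative, and a site cannot follow both. Appendix B matters in practice because Section 3.6 sends readers there for the procedures at each visit, so a coordinator working from it would draw blood at baseline and week 4. Table 2 schedules no other blood sample at either visit. The affected patients are minors, and the draws would come on top of the total of approximately 35 mL stated for each patient.

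The baseline visit raises a second, practical point. Inclusion criterion j requires a negative HCG test at baseline, Section 5.9 has patients randomized "after confirmation of all eligibility criteria", and footnote a of Table 2 says the baseline visit "will occur the same day as the scheduled first dose of the IMP". A serum test at that visit could make same-day randomization and dosing wait for a laboratory result.

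**Working it through.** **Test matrix by visit**

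| Visit | Appendix B | Protocol Table 2, footnote n | SAP Table 2, footnote n | SAP 9.6 |
|---|---|---|---|---|
| Screening | serum | serum | serum | serum |
| Baseline | serum | urine | urine | urine |
| Week 4 | serum | urine | urine | not mentioned |
| Week 8 | serum | serum | serum | serum |
| Unscheduled | serum | serum, if clinically indicated | serum, if clinically indicated | not mentioned |

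Two of the five Appendix B entries conflict with footnote n. The other three agree with it.

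**Which text is wrong**

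- Section 7.5.2.1 allows for both serum and urine and refers to Table 2. If every test were serum, as in Appendix B, its mention of urine would have no use.
- The SAP supports urine at baseline in two places (Table 2 footnote n and Section 9.6). For week 4 it does so in one (footnote n).
- The blood-volume table points the same way, as shown next.

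**The plan's own blood total**

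Inputs, from Table 4 in Section 5.11: clinical laboratory 10 mL × 2; pharmacokinetic 5 mL × 2; CYP2D6 genotyping 3 mL × 1; optional pharmacogenetic sample 2 mL × 1.

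Total = (10 × 2) + (5 × 2) + 3 + 2 = 20 + 10 + 3 + 2 = 35 mL, which reproduces the stated figure.

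HCG blood is counted inside the two clinical laboratory samples. Table 2 and Section 9.7 place those at screening and week 8 only. The 35 mL therefore contains nothing for baseline or week 4.

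**Effect of following Appendix B**

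- Visits with a scheduled blood draw: 2 under Table 2 (screening, week 8); 2 + 2 = 4 under Appendix B (adding baseline and week 4).
- Volume: 35 + 2v mL, where v is the volume of one stand-alone serum HCG sample. The documents do not give v. The range below is an assumption; 2 and 10 mL are the smallest and largest sample volumes in Table 4.

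| Assumed v (mL) | 35 + 2v (mL) | Increase, 2v/35 |
|---|---|---|
| 2 | 39 | 11% |
| 3 | 41 | 17% |
| 5 | 45 | 29% |
| 10 | 55 | 57% |

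**The case against.** The strongest reply is that the protocol already resolves the conflict. Section 7.5.2.1 refers to Table 2, Section 3.6 presents Table 2 as the schedule and Appendix B as a listing by visit, and the Amendment 02 summary says Appendix B was updated to match the schedule. On that reading this is a copying slip with an evident master text. That is right about intent, and it is why the point is minor. It does not protect a site that works from Appendix B alone.

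The volume range is open to challenge. The 2 mL figure belongs to the pharmacogenetic sample and the 10 mL figure to a whole laboratory draw, which HCG testing shares with the chemistry and hematology panels. Nothing in the documents supports 10 mL for HCG alone, so the upper end is an outer bound. The firm statement is 35 + 2v. The 35 mL is also approximate and not a cap: Table 4 does not count the blood that Sections 7.1.5 and 7.1.7 allow for when a patient stops because of an adverse event. Exceeding it would make a stated total inaccurate without breaching a limit.

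The delay at baseline is only a possibility. No turnaround time is given, criterion j does not name a test matrix, and a serum test would satisfy it. No loss of safety or eligibility follows.

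The absence of week 4 from protocol Section 9.7 and SAP Section 9.6 is a separate omission and says nothing about serum or urine.

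One possible defense of Appendix B fails. Its baseline text says certain scales come before blood draws, which might suggest that blood was planned at that visit. The same sentence appears under the telephone contacts at weeks 1, 3 and 6, and under weeks 2 and 9, where Table 2 schedules no blood.

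**Conclusion.** The concern holds. Appendix B is wrong as written at baseline and week 4, and urine is the intended test at both visits. The certain consequence for a site that follows Appendix B is two added venipunctures for each girl who is postmenarchal or aged 12 and over; the documents do not say how many such patients are expected. The added volume cannot be fixed without v, and any delay at baseline is unknown. The effect is operational only, and the severity is minor.

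**What to change.** In Appendix B, change serum to urine in item 3 (baseline) and item 4c (week 4), and send sites a short note. Leave the screening, week 8 and unscheduled entries, Table 2 and Table 4 as they are. As optional tidying, name the week 4 urine test in protocol Section 9.7 and SAP Section 9.6. The cost is two words and the note.

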APPENDIX C.QUALITY CONTROL AND QUALITY ASSURANCE

Protocol Amendments and Protocol Deviations

Protocol Amendments

No changes from the final approved (signed) protocol will be initiated without the prior written approval or favorable opinion of a written amendment by the IEC/IRB and national and local competent authorities, as applicable, except when necessary to address immediate safety concerns to the patients or when the change involves only nonsubstantial logistics or administration. The principal investigator at each investigational center, the coordinating investigator (if applicable), and the sponsor will sign the protocol amendment.

Protocol Deviations

Any deviation from the protocol that affects, to a significant degree, (a) the safety, physical, or mental integrity of the patients in the study and/or (b) the scientific value of the study will be considered a protocol violation. Protocol deviations may include non-adherence on the part of the patient, the investigator, or the sponsor to protocol-specific inclusion and exclusion criteria, primary objective variable criteria, or GCP guidelines; noncompliance to IMP administration; use of prohibited medications. Protocol deviations will be identified and recorded by investigational center personnel in the CRF. All protocol deviations will be reported to the responsible IEC/IRB, as required.

When a protocol violation is reported, the sponsor will determine whether to withdraw the patient from the study or permit the patient to continue in the study, with documented approval from the medical expert. The decision will be based on ensuring the safety of the patient and preserving the integrity of the study.

Changes in the inclusion and exclusion criteria of the protocol are **not** prospectively granted by the sponsor. If investigational center personnel learn that a patient who did not meet protocol inclusion and exclusion criteria was entered in a study, they must immediately inform the sponsor of the protocol violation. If such patient has already completed the study or has withdrawn early, no action will be taken but the violation will be recorded.

Information to Study Personnel

The investigator is responsible for giving information about the study to all personnel members involved in the study or in any element of patient management, both before starting the study and during the course of the study (eg, when new personnel become involved). The investigator must ensure that all study personnel are qualified by education, experience, and training to perform their specific task. These study personnel members must be listed on the investigational center authorization form, which includes a clear description of each personnel member's responsibilities. This list must be updated throughout the study, as necessary.

The study monitor is responsible for explaining the protocol to all study personnel, including the investigator, and for ensuring they comply with the protocol.

Study Monitoring

To ensure compliance with GCP guidelines, the study monitor or representative is responsible for ensuring that patients have signed the informed consent form and the study is conducted according to applicable Standard Operating Procedures (SOPs), the protocol, and other written instructions and regulatory guidelines.

The study monitor is the primary association between the sponsor and the investigator. The main responsibilities of the study monitor(s) are to visit the investigator before, during, and after the study to ensure adherence to the protocol, that all data are correctly and completely recorded and reported, and that informed consent/assent, depending on the child's age, as appropriate, is obtained and recorded for all patients before they participate in the study and when changes to the consent form are warranted, in accordance with IEC/IRB approvals.

The study monitor(s) will contact the investigator and visit the investigational center according to the monitoring plan. The study monitor will be permitted to review and verify the various records (CRFs and other pertinent source data records, including specific electronic source document relating to the study) to verify adherence to the protocol and to ensure the completeness, consistency, and accuracy of the data being recorded.

As part of the supervision of study progress, other sponsor personnel may, on request, accompany the study monitor on visits to the investigational center. The investigator and assisting personnel must agree to cooperate with the study monitor to resolve any problems, errors, or possible misunderstandings concerning the findings detected during the course of these monitoring visits or provided in follow-up written communication.

Audit and Inspection

The sponsor may audit the investigational center to evaluate study conduct and compliance with protocols, SOPs, GCP guidelines, and applicable regulatory requirements. The sponsor's Global Clinical Quality Assurance, independent of Global Specialty Development, is responsible for determining the need for (and timing of) an investigational center audit.

The investigator must accept that competent authorities and sponsor representatives may conduct inspections and audits to verify compliance with GCP guidelines.

APPENDIX D.ETHICS

Informed Consent/Assent

The investigator, or a qualified person designated by the investigator, should fully inform the patient and parent/legally acceptable representative of all pertinent aspects of the study, including the written information approved by the IEC/IRB. All written and oral information about the study will be provided in a language as nontechnical as practical to be understood by the patient. The patient should be given ample time and opportunity to inquire about details of the study and to decide whether or not to participate in the study. The above should be detailed in the source documents.

A personally signed and dated informed consent will be obtained from the parent/legally acceptable representative, and a signed and dated assent, depending on the child's age, as appropriate, will be obtained from each patient (if the patient is able) before any study specific procedures or assessments are done and after the aims, methods, anticipated benefits, and potential hazards are explained. The patient's willingness to participate in the study will be documented in the informed consent form, which will be signed and personally dated by the patient and by the person who conducted the informed consent discussion. The investigator will keep the original informed consent/assent forms, depending on the child's age, as appropriate, and copies will be given to the patients. It will also be explained to the patients that the patient is free to refuse participation in the study and free to withdraw from the study at any time without prejudice to future treatment.

The investigator, or a qualified person designated by the investigator, should fully inform the patient and each parent/legally acceptable representative of all pertinent aspects of the study, including the written information approved by the IEC/IRB. All written and oral information about the study will be provided in a language as nontechnical as practical to be understood by the each parent/legally acceptable representative and the patient. The patient and each parent/legally acceptable representative should be given ample time and opportunity to inquire about details of the study and to decide whether or not to participate in the study. The above should be detailed in the source documents.

A personally signed and dated informed consent form will be obtained from each parent/legally acceptable representative, and a signed and dated assent and/or co-consent form will be obtained from each patient (if the patient is able) before any study specific procedures or assessments are done and after the aims, methods, anticipated benefits, and potential hazards are explained; according to IEC/IRB requirements. The forms will be signed and dated also by the person who conducted the informed consent discussion. The investigator will keep the original informed consent and assent forms, and copies will be given to the patients (and each parent/legally acceptable representative). It will also be explained to the patients (and each parent/legally acceptable representative) that they are free to refuse participation in the study and free to withdraw from the study at any time without prejudice to future treatment.

Competent Authorities and Independent Ethics Committees/Institutional Review Boards

Before this study starts, the protocol will be submitted to the national competent authority and to the respective IEC/IRB for review. As required, the study will not start at a given investigational

center before the IEC/IRB and competent authority (as applicable) for the investigational center give written approval or a favorable opinion.

Confidentiality Regarding Study Patients

The investigator must ensure that the privacy of the patients, including their identity and all personal medical information, will be maintained at all times. In CRFs and other documents or image material submitted to the sponsor, patients will be identified not by their names, but by an identification number.

Personal medical information may be reviewed for the purpose of patient safety or for verifying data in the source and the CRF. This review may be conducted by the study monitor, properly authorized persons on behalf of the sponsor, Global Quality Assurance (GCA), or competent authorities. Personal medical information will always be treated as confidential.

Registration of the Clinical Study

In compliance with national and local regulations and in accordance with Teva standard procedures, this clinical study will be registered on trials registry websites.

